- Patient accrual is targeted at one patient per month during the first 6 months and 1-2 patients every 1-2 months afterwards, and follow-up period after completing accrual will be 12 months post treatment.
- Based on a power of 84% and type 1 error (1-sided) of 0.15, a total of 49 subjects will need to be accrued.
- Allowing for a proportion of the subjects not being evaluable, a maximum of 54 subjects will be accrued.

SCHEMA

[figure not shown]

TABLE OF CONTENTS

PRÉCIS	2
SCHEMA	4
TABLE OF CONTENTS.....	5
1 OBJECTIVES	8
1.1 Primary Objective	8
1.2 Secondary Objectives.....	8
1.3 Exploratory Objectives	8
2 BACKGROUND	8
3 PATIENT SELECTION	11
3.1 Eligibility Criteria	11
3.2 Recruitment Strategies.....	14
3.3 Screening Evaluation	15
3.4 Baseline Evaluation	15
3.5 Accrual Estimates	16
4 REGISTRATION PROCEDURES	17
4.1 General Guidelines.....	17
4.2 Registration Procedures	17
4.3 Randomization Procedures	17
5 TREATMENT PLAN.....	18
5.1 Study Design.....	18
5.2 Trial Outline.....	19
5.3 Agent Administration.....	21
5.4 Dose Limiting Toxicity.....	22
5.5 General Concomitant Medication and Supportive Care Guidelines.....	24
5.6 Duration of Therapy.....	25
5.7 Duration of Follow Up.....	25
5.8 Criteria for Removal from Protocol Therapy and Off Study Criteria.....	25

6	DOSING DELAYS/DOSE MODIFICATIONS	27
6.1	TICE BCG	27
6.2	PANVACTM-V (vaccinia) and PANVACTM-F (fowlpox)	27
7	NIH REPORTING REQUIREMENTS / DATA AND SAFETY MONITORING PLAN	28
7.1	Definitions.....	28
7.2	OHSRP Office of Compliance and Training / IRB Reporting	29
7.3	NCI Clinical Director Reporting.....	29
7.4	NCI Guidance for Reporting Expedited Adverse Events for Multi-Center Trials	29
7.5	NIH Office of Science Policy (OSP)/Institutional Biosafety Committee (IBC) Reporting Criteria	30
7.6	NIH Required Data and Safety Monitoring Plan.....	31
8	ADVERSE EVENTS: LIST AND SPONSOR REPORTING REQUIREMENTS	31
8.1	Comprehensive Adverse Events and Potential Risks List(s) (CAEPRs).....	32
8.2	Definitions.....	38
8.3	Expedited Adverse Event Reporting to CTEP	39
8.4	Routine Adverse Event Reporting to CTEP	42
8.5	Secondary Malignancy.....	42
8.6	Second Malignancy.....	43
9	PHARMACEUTICAL INFORMATION.....	43
9.1	CTEP IND Agents	43
9.2	Commercial agent	59
10	BIOMARKER, CORRELATIVE, AND SPECIAL STUDIES	60
10.1	Laboratory Correlative Studies	60
10.2	Sample Storage, Tracking and Disposition.....	66
11	STUDY CALENDARS	68
12	MEASUREMENT OF EFFECT	73
12.1	Response Criteria	73

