1 OBJECTIVES

1.1 PRIMARY OBJECTIVE

1.1.1 To determine if there is an improvement in disease-free survival (DFS*) with BCG + PANVAC compared with BCG alone in a phase II study in non-muscle invasive high-grade urothelial carcinoma of the bladder who have failed to respond to intravesical BCG. *within 1 year post treatment

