5.7 DURATION OF FOLLOW UP

Subjects will be followed for 1 year after the initial 20 week study course is completed with surveillance cystoscopy or until death, whichever occurs first.

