5.8.2 Off-Study Criteria

- Completed study follow-up period (1 year post treatment)
- Disease progression to muscle-invasive urothelial carcinoma of the bladder
- Subject's request to be taken off study. In this event, the reasons for withdrawal will be documented.
- If subjects are non-compliant with the protocol guidelines, they may be removed from the study at the discretion of the principal investigator.
- Death

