Patient accrual is targeted at one patient per month during the first 6 months and 2 patients per month afterwards, and follow-up period after completing accrual will be 12 months. The power calculation was based on one-sided log-rank test at 15% significance level. Sample size, power and duration of the study are presented in the table below. With a total number of 49 patients, the power is 84% (see table below). Under this scenario, the expected number of events (recurrence or death) is 40. In order to allow for the possibility of a small number of unevaluable patients, the accrual ceiling will be set at 54 patients.

	Subgroup 1 1-year recurrence-free survival for BCG persistent patients who failed 1 BCG induction course	Subgroup 2 1-year recurrence-free survival for BCG persistent patients who failed 2 or more BCG induction courses	Subgroup 3 1-year recurrence-free survival for BCG naïve patients	Total sample size	Power (%)	Duration of accrual (months)	Expected number of events (recurrence or death)
Treatment benefit	HR=2.277 1-year RFS: BCG alone: 37.5% BCG+PANVAC: 65%	HR=2 1-year RFS: BCG alone: 20% BCG+PANVAC: 44.7%	HR=1.7 1-year RFS: BCG alone: 48% BCG+PANVAC: 65%	49	84	28	40

One interim analysis for futility will be performed according to the stopping procedure.³⁹ Specifically, the interim analysis will be performed when half of the expected events (20) have been observed. At that time, if the observed event rate of the TICE BCG+PANVAC arm is higher than that of the TICE BCG alone arm (i.e. the hazard ratio ≥ 1), we would consider terminating the trial and concluding that an advantage for the BCG+PANVAC regimen has not been established.

For the purpose of protecting patient safety, we implement the following stopping rule for safety monitoring of patients who receive the combination therapy.

If one patient experiences a grade 5 event, thought to be possibly or probably due to the combination therapy, the study will be stopped. For grade 3 or 4 event, the study will be stopped according to the following stopping rule. These adverse events are described in more detail in Section 7.

Number of patients	No. of grade 3 or 4 serious adverse events
3-9	3
10-18	4
19-26	5

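### The 40 expected events in Section 14.1 presuppose follow-up to a common cut-off; under the protocol's own per-patient limit about 34-35 are expected, so 20 events is not half

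*Combined protocol and SAP*

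**What the plan says.** **Design calculation (Section 14.1).** Accrual is one patient a month for 6 months and two a month thereafter, with 12 months of follow-up after accrual closes. The table gives 28 months of accrual. On the test: "The power calculation was based on one-sided log-rank test at 15% significance level". On the result: "With a total number of 49 patients, the power is 84% (see table below". On events: "Under this scenario, the expected number of events (recurrence or death) is 40". The futility look is tied to that count: "the interim analysis will be performed when half of the expected events (20) have been observed". No per-patient limit on follow-up is mentioned.

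**Précis.** It repeats the result: "Based on a power of 84% and type 1 error (1-sided) of 0.15, a total of 49 subjects will need to be accrued". It gives follow-up after accrual as 12 months post treatment, whereas Section 14.1 says only 12 months.

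**Follow-up as it will be conducted.** Section 5.7: "Subjects will be followed for 1 year after the initial 20 week study course is completed with surveillance cystoscopy", or until death if earlier. Section 5.8.2 lists among the off-study criteria "Completed study follow-up period (1 year post treatment". Section 5.1.6 and calendar footnote 10 also give one year of three-monthly visits after the 20-week course, and 5.1.6 leaves later surveillance to outside urologists.

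**Endpoint.** The primary objective (1.1) limits disease-free survival (DFS) to "within 1 year post treatment" without saying where the year starts. Section 12.1.1.3 measures recurrence-free survival (RFS) from the start of BCG in week 3.

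**The concern.** Two follow-up schemes stand in one protocol. The calculation in 14.1 sets a calendar end for the whole trial, so patients who enter early contribute up to about 39.5 months. The conduct sections set a fixed period per patient, and nothing provides for study follow-up beyond it. An event count derived under the first scheme includes events that the second will not record.

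Two things rest on that count. The expected number of events describes how much information the trial will yield, and the futility look is defined as half of it. If the count is too high, a reader of the final report will see a shortfall that was built into the plan, and the information fraction at the interim is misdescribed.

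**Working it through.** **Inputs** (14.1 unless stated). Exponential RFS in both arms. Subgroup mix 1:5:1, so 7, 35 and 7 of 49. Equal allocation (4.3), so 3.5, 17.5 and 3.5 per arm. One-year RFS, BCG alone against combination: 37.5% / 65%, 20% / 44.7%, 48% / 65%. Accrual lasts 6 + 43/2 = 27.5 months (28 in the table). No loss to follow-up is assumed.

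**Formula.** With monthly hazard λ = −ln(1-year RFS)/12, a group of n patients each followed for f months gives n × (1 − e^(−λf)) expected events. Where follow-up varies evenly from a to b months, the mean event-free fraction is (e^(−λa) − e^(−λb)) / (λ(b − a)).

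**Reproducing the 40.** Take a common cut-off at month 28 + 12 = 40. The first 6 patients have 34-40 months and the other 43 have 12.5-34 months. For subgroup 2, BCG alone, λ = 1.6094/12 = 0.1341. The event-free fractions are 0.0072 and 0.0612, and their weighted mean is (6 × 0.0072 + 43 × 0.0612)/49 = 0.0546. Events are 17.5 × 0.9454 = 16.54. The other cells follow in the same way.

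**Protocol limit.** One year after week 20, counted from BCG start in week 3, is 12 months + 17 weeks = 15.9 months. For subgroup 2, BCG alone: 17.5 × (1 − 0.20^(15.91/12)) = 17.5 × 0.8816 = 15.43.

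| Subgroup, arm | n | Common cut-off, month 40 | All followed 15.9 months | All followed 12 months |
|---|---|---|---|---|
| 1, BCG alone | 3.5 | 2.96 | 2.55 | 2.19 |
| 1, combination | 3.5 | 2.02 | 1.52 | 1.22 |
| 2, BCG alone | 17.5 | 16.54 | 15.43 | 14.00 |
| 2, combination | 17.5 | 13.80 | 11.48 | 9.67 |
| 3, BCG alone | 3.5 | 2.66 | 2.18 | 1.82 |
| 3, combination | 3.5 | 2.02 | 1.52 | 1.22 |
| **Total** | 49 | **40.0** | **34.7** | **30.1** |

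With accrual at exactly 27.5 months the common cut-off gives 39.7.

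**Range over readings of the limit:**
- Counted from week 3, the last entrants cut at 12 months after accrual ends: 34.3-34.4. Everyone completing the full period: 34.7.
- Counted from week 0 (12 months + 20 weeks = 16.6 months): 34.9-35.0, or 35.3 if everyone completes.
- DFS window of 1 year from the last BCG dose (week 8): 31.6. From the last PANVAC dose (week 15): 33.3-33.4. From BCG start: 30.1.

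**Information at the look.** 20/40 = 50% as stated. 20/35.0 = 57% and 20/34.3 = 58% under the limit. 20/30.1 = 66% only if DFS is cut 12 months after BCG start.

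**Power.** Simulated trials, one-sided 15% log-rank (critical value 1.036), unstratified; the stop applies if the combination arm is doing no better at event 20.

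| Follow-up | Without stop | With stop at 20 | With an earlier look |
|---|---|---|---|
| Common cut-off | about 85% | about 82% | – |
| 1 year after week 20 | 82-83% | 80-81% | about 79% at 17 events |
| 12 months from BCG start | about 79% | about 78% | about 76% at 15 events |

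Section 14.1 does not say whether the log-rank test is stratified. A stratified test adds about a point: 85.8% with the common cut-off, and 83.2-83.9% under the protocol limit.

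**The case against.** **The 84% does not depend on long follow-up.** This stands. By the Schoenfeld formula at a hazard ratio of 2, power is Φ(½ × √D × ln 2 − 1.036). For D = 40 that is Φ(1.156) = 87.6%, and for D = 34 it is Φ(0.985) = 83.8%. The stated 84% is compatible with either follow-up scheme, and the simulated loss is small beside the uncertainty in the assumed rates and the 1:5:1 mix. A reader might infer that the trial is materially underpowered; the figures do not show that.

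**Nothing waits for 40 events.** This also stands. Section 14.1 fixes the end of the trial by time, so the inference that the trial could stall short of an event target has no basis in the text. The interim trigger is an explicit 20 and can be carried out as written.

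**34 is not a ceiling.** Correct. It is an expectation, and a few per cent of simulated trials under the limit still reach 40.

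**30 events is the least favourable reading.** Correct. It starts the year at the beginning of BCG, while the objective says post treatment.

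**Footnote 10 might seem to supply the longer follow-up.** It does not. It lets outside records stand in for three-monthly visits within the same one-year schedule, not up to a later common date.

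None of this reconciles the event count with the conduct sections. Every reading of the per-patient limit stays well below 40.

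**Conclusion.** The event count is wrong for the follow-up that the protocol prescribes. Forty belongs to a common cut-off; the protocol's limit gives about 34-35, a shortfall of (40 − 35.3)/40 = 12% to (40 − 34.3)/40 = 14%. If the DFS window runs from the last BCG or last PANVAC dose, about 32-33 are expected, and about 30 if it runs from BCG start. Describing 20 events as half is wrong for the same reason.

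The consequence for power is minor: 82-83% without the futility stop and 80-81% with it, against 84% stated. Only cutting DFS at 12 months from BCG start brings it to about 79% / 78%.

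These results assume the plan's exponential rates, subgroup mix and accrual, 49 evaluable patients and no loss to follow-up. The ceiling of 54 is there for unevaluable patients and does not remove the mismatch.

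**What to change.** **Preferred.** In Section 14.1, its table and the précis, state about 34-35 expected events and about 82-83% power (80-81% with the futility stop), and name the follow-up limit that these figures assume. Bring the précis and 14.1 descriptions of follow-up after accrual into line. In 1.1, define the time origin of the 1-year DFS window; if the window is shorter than 1 year after week 20, use the matching figures above.

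Keep the futility look at 20 events and describe it as about 57-58% of the expected events. A reader might think that the look should move to 17 or 15 to restore one half. That would lower power with the stop to about 79%, or to about 76% under the 12-month reading, for no gain.

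**Alternative.** To keep 40, amend 5.7 and 5.8.2, with 5.1.6 and footnote 10 to match, so that recurrence and death are collected for all patients to a common cut-off 12 months after accrual ends. The current text does not provide for this.

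**Cost.** The preferred route is an edit to the wording and the table, with a stated power that is slightly less favourable. The alternative adds data collection for patients who enter early. Neither needs extra patients or changes the test or its significance level.

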5.4 DOSE LIMITING TOXICITY

TICE BCG will be given in the standard dose and schedule as described above. All toxicities observed will be tabulated by maximum grade per subject. A dose limiting toxicity (DLT) will be any grade 3 or greater adverse effect (AE) by CTCAE v5.0 related to the investigational agent and persisting for more than one week and not improving by routine standard of care. In

addition, any grade 3 or greater AE as per a previously published vaccinia toxicity grading scale³³ related to the investigational agent will also be considered a DLT.

Intravesical BCG therapy can lead to common side effects that are usually self-limited, particularly with dose reduction. These side effects include, but are not limited to, gross hematuria, dysuria, frequency, urgency, bladder spasms, and generalized cystitis. These side effects will not be considered a DLT if it is related to BCG and resolves with BCG dose reduction and/or postponing therapy by 1-2 weeks and treating symptoms with conservative management. In contrast, persistent side effects despite dose reduction/postponing of BCG therapy or the development of systemic BCG infection (aka “BCG-osis”) will be considered a DLT.

Severe adverse events due to local instillation of BCG are uncommon. In a retrospective analysis of 2602 patients reported in 1989, the overall rate of serious complications was less than five percent.³⁴ The most common complication was fever >103°F in 2.9 percent followed in decreasing frequency by:

- Significant hematuria (1 percent)
- Granulomatous prostatitis (0.9 percent)
- Pneumonitis and/or hepatitis (0.7 percent)
- Arthralgia (0.5 percent)
- Epididymitis (0.4 percent)
- Sepsis (0.4 percent)
- Rash (0.3 percent)
- Ureteral obstruction (0.3 percent)
- Contracted bladder (0.2 percent)
- Renal abscess (0.1 percent)
- Cytopenia (0.1 percent)

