Systemic sepsis and even death can also develop early following local instillation of BCG. During the initial clinical experience with BCG as an intravesical agent, most cases of sepsis could be traced back to recognized errors in BCG administration such as traumatic catheterization, administration too early after transurethral surgery, or instillation during a concomitant UTI. All these conditions result in physical disruptions in the urothelial blood barrier. Sepsis has been estimated to occur in approximately one in every 15,000 patients treated with intravesical BCG.³⁴ Prompt recognition and administration of multidrug, antibiotic therapy is necessary if true BCG sepsis occurs.

- 5.4.1 For the purpose of protecting subject safety, we implement the following stopping rule for safety monitoring of subjects who receive the combination therapy.
- 5.4.2 If one subject experiences a grade 5 event, thought to be possibly or probably due to the combination therapy (PANVAC + BCG), the study will be stopped. For grade 3 or 4

events probably related to the investigational agent (PANVAC) and persisting for more than one week and not improving by routine standard of care, the study will be stopped according to the stopping rule described in Section 14.

5.4.2.1 The exceptions to what constitute true adverse events/DLTs are previously noted.

5.4.3 Formal dose escalation/Phase I study is not planned as the TICE BCG doses are consistent with standard of care and the TICE BCG is being administered in an intravesical fashion while the PANVAC™ is given subcutaneously and in doses that have been shown to be safe in multiple Phase I and Phase II studies in a variety of different cancers.

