The operating characteristic of the stopping rule was assessed by simulations. Based on 10,000 simulations, the probability of stopping early for an excess of serious adverse event over the course of trial is 0.04 when the serious adverse event rate is at the anticipated level of 6% and 0.94 when the serious adverse event rate is 30%. This is deemed reasonable for protecting patient safety.

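### Sections 5.4.2 and 14.1 tie one safety stopping boundary to different grade 3-4 events, so the same data can give opposite stop decisions

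*Combined protocol and SAP*

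**What the plan says.** **Section 5.4.2** limits the grade 3-4 stopping rule to "events probably related to the investigational agent (PANVAC) and persisting for more than one week and not improving by routine standard of care", and for such events "the study will be stopped according to the stopping rule described in Section 14". It has no boundary of its own and does not require the event to be serious. Section 5.4.2.1 adds: "The exceptions to what constitute true adverse events/DLTs are previously noted". The relevant exception, in Section 5.4, concerns common BCG effects such as haematuria, dysuria and cystitis: "These side effects will not be considered a DLT if it is related to BCG and resolves with BCG dose reduction" or with a short postponement and symptomatic care.

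**Section 14.1** prints the boundary: 3 events in 3-9 patients, 4 in 10-18, 5 in 19-26, for patients on the combination. The introductory sentence reads "For grade 3 or 4 event, the study will be stopped according to the following stopping rule". The table column is headed "No. of grade 3 or 4 serious adverse events". The next sentence says "These adverse events are described in more detail in Section 7". The simulation paragraph gives an early-stopping probability of "0.04 when the serious adverse event rate is at the anticipated level of 6" per cent, and 0.94 at 30%, both labelled as serious adverse event rates. Section 14.1 does not refer to Section 5.4.

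**The concern.** A mandatory stopping rule has to give one answer for one set of data. Here a single boundary is attached to an event that is narrow in one section (attributed to PANVAC, persistent, BCG effects removed) and broad in the other (any grade 3-4 event in the text, any serious one in the table). Both arms receive BCG, whose irritative toxicity is common, so the excluded events are ones the trial should expect to see.

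There are two consequences. The trial could be halted for ordinary BCG toxicity, or continue past a PANVAC signal, depending on which section is in hand. And because treatment is open label, the choice would be made by people who have already seen the events. The operating characteristics are also presented for one event only, so they cannot support both rules.

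**Working it through.** **1. Reproducing the plan's figures.** Inputs: the boundary and the 6% and 30% rates from Section 14.1. Assume one yes/no event per patient with probability p, independent patients, 26 combination-arm patients, and a check after each patient from the third. Let b(n) = 3 for n = 3-9, 4 for n = 10-18 and 5 for n = 19-26. Let f_n(x) be the probability of reaching patient n with x events and no stop:

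f_n(x) = f_{n-1}(x)(1-p) + f_{n-1}(x-1)p

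Any probability at x ≥ b(n) is moved to stopping. Within a band the threshold is constant and the count cannot fall, so this equals looking at n = 9, 18 and 26 only.

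The first band by hand is 1 - [(1-p)^9 + 9p(1-p)^8 + 36p²(1-p)^7]:
- p = 0.06: 1 - (0.5730 + 0.3292 + 0.0840) = 0.014
- p = 0.11: 1 - (0.3504 + 0.3897 + 0.1927) = 0.067

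Cumulative stopping probability from the full recursion:

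| p | by patient 9 | by patient 18 | by patient 26 |
|---|---|---|---|
| 6% | 0.014 | 0.027 | 0.0345 |
| 11% | 0.067 | 0.148 | 0.2005 |
| 30% | | | 0.939 |

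The stated 0.04 and 0.94 are consistent with this; 400,000 simulations gave 0.034, 0.200 and 0.939. Reading the table as stop when the count exceeds the boundary gives 0.006 and 0.851, which does not fit. So the rule stops on reaching 3, 4 or 5, and the boundary is sound for one well-defined event.

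**2. The event definitions side by side.**

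| Condition | 5.4.2 | 14.1 text | 14.1 table and simulation |
|---|---|---|---|
| Grade | 3-4 | 3-4 | 3-4 |
| Probably related to PANVAC | yes | not stated | not stated |
| Over a week, not improving | yes | not stated | not stated |
| Self-limited BCG effects excluded | yes | not stated | not stated |
| Serious | not required | not stated | yes |

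The pointer to Section 7 does not help: that section covers NIH reporting and monitoring, and Section 7.1 refers definitions to an outside policy. Section 5.3 makes the same reference, so it may be an old number for Section 8. But Section 8.3.2 defines seriousness by outcome and requires reporting regardless of relatedness, which still differs from 5.4.2.

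**3. The same data under each section.**
- *Case A.* Three of the first 9 combination patients are hospitalised for at least 24 hours with BCG-attributed grade 3 haematuria that resolves within days once BCG is held. Text and table of 14.1: count 3, stop. Section 5.4.2: count 0, continue.
- *Case B.* Three of the first 9 have grade 3 injection site reactions (foreseen in Section 6.2.1), probably due to PANVAC, lasting over a week, not improving, with no hospitalisation. Section 5.4.2: count 3, stop. Table of 14.1: count 0, continue, unless they are judged important medical events. Under the 14.1 sentence taken alone the count is also 3, so this case rests on the table heading.

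**4. Size under the 14.1 text.** The BCG table in Section 8.1.2.1 lists dysuria in 401 of 674 patients (401/674 = 59.5%, matching the printed 60%), with grade 3 or higher in 11%. The rate of any grade 3-4 event in that series is therefore at least about 11%. If the combination arm has at least that rate, the stopping probability is at least about 0.20, roughly six times that at 6% (0.2005/0.0345 = 5.8). For 10.5% to 11.5% it is 0.178 to 0.224. At 11% with 24, 25 and 27 patients it is 0.177, 0.188 and 0.214.

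**5. Size when the definitions are nested (assumed inputs).** The documents do not say what share f of 14.1 events would also meet 5.4.2. If the 5.4.2 events are a subset of the 14.1 events, whose rate is q, the difference in stopping probability is the chance that the two sections disagree:

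| q | 14.1 | 5.4.2, f = 0.75 | f = 0.5 | f = 0.25 | Chance of disagreement |
|---|---|---|---|---|---|
| 10% | 0.156 | 0.069 | 0.019 | 0.002 | 0.087 to 0.154 |
| 20% | 0.665 | 0.409 | 0.156 | 0.019 | 0.256 to 0.646 |
| 30% | 0.939 | 0.765 | 0.409 | 0.069 | 0.174 to 0.870 |

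**The case against.** The best defence is that the sections can be harmonised. Section 5.4.2 gives the full event and borrows only the numbers from Section 14; 14.1 repeats the grade 5 clause almost unchanged and reads like a shortened restatement. The unconditioned 14.1 sentence also leads straight into a table headed with serious events, so 14.1 arguably contains one definition, not two. The 0.20 then attaches to the least likely reading: grade 3 dysuria need not be serious, 5.4.2 would exclude it if it resolved, and the grading scale of the BCG series is not given. Case B depends on one heading and on no important-medical-event judgement. The pause after the first six combination patients (Section 5.1) and the Safety Monitoring Committee (Section 7.6.2) give separate review. The study closed with CTEP in May 2019, so an edit may now have little prospective effect.

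Much of this stands as a limit on size: 0.20 belongs only to the literal 14.1 text, and Case B is conditional. It does not remove the conflict. Section 14.1 never points to 5.4, adds a seriousness condition that 5.4.2 lacks, and states attribution for grade 5 events but not for grade 3-4, so its reader can fairly conclude that none is needed. Case A gives opposite decisions whether 14.1 is read by its text or its table. The other safeguards do not say which events count.

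**Conclusion.** The concern holds. The plan contains two conflicting rules for a mandatory safety stop and does not say which governs. The boundary and its stated probabilities are correct for a single event at 6% or 30%, but the plan labels those as serious adverse event rates and gives no anticipated rate for the 5.4.2 event, so the 0.04 and 0.94 are not shown to apply to it. Under the 14.1 sentence as written, the stopping probability is about 0.20 at an 11% rate (0.18 to 0.22 for 10.5% to 11.5%), assuming the combination arm has at least the grade 3 or higher dysuria rate of the BCG series. For the serious-event reading, the documents do not give the overlap needed to put a figure on the disagreement. The primary efficacy analysis is not affected. This should be fixed.

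**What to change.** - In Section 14.1, replace the event in both the text and the table heading with the 5.4.2 definition, including the Section 5.4 exceptions, counted as combination-arm patients with at least one qualifying event.
- Change the reference from Section 7 to Section 5.4.
- State that 6% and 30% are rates of that event. If its anticipated rate is not 6%, re-run the simulation and report the new probabilities.
- If the sponsor prefers the broader serious-event definition, use it in 5.4.2 as well, so that both sections match.
- If treatment is already complete, state in the report which definition was applied.

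The cost is a few sentences, plus at most one re-run of an existing simulation.
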